3. STUDY DESIGN

A placebo-controlled multi-center adaptive randomized controlled trial, see figure 2 for the logistics of the study.

Figure 2: Study design of the trial

a. Duration of Follow-Up

The duration of follow-up for each participant depends on the interim results of the primary endpoint and the probability of obtaining a result, with a maximum of 168 days. The end of the study is defined as the last patient's last registration in the mobile application. Study participants will collect fingerstick dried blood spot (DBS) samples for serology testing at baseline, weeks 4, 8, 12, 16, 20 and 24. If they develop symptoms, they will be qPCR tested by nasopharyngeal swab, oral swab and/ or fecal swabs.

[figure not shown]

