Participants will complete intermittent surveys via an electronic system every 7 days to assess the presence of any flu-like symptom, including sore throat, fever, headache, malaise, and cough. Note that this is part of routine surveillance for Covid-19 in health workers at the United States site. Consent forms will ask for consent to access this survey information.

Any positive response on the survey will trigger a nasopharyngeal, oral and/ or rectal swab to be collected to test for Covid-19 via rt-PCR

All participants, regardless of survey responses, will have serology for Covid-19 tested at 4 week intervals during the follow-up period (6 months)

If a participant completes the follow-up period and does not test positive for disease, their study participation is complete

If a participant does test positive for disease, their disease status will be ascertained for up to two months or until an outcome is available through one of the following mechanisms: (1) an electronic survey if they are not admitted to the hospital, including questions about the number of days they are ill, daily fever, and other symptoms; or (2) if they are admitted to the hospital, ordinal outcomes for disease severity will be extracted from the hospital's electronic medical records system.

During the first week of follow-up, all participants will actively be asked about any adverse events; thereafter, participants will report unsolicited AEs through the electronic survey. Vaccine related adverse events will be graded using the FDA guidance (<https://www.fda.gov/media/73679/download>) and noted using WHO-recommended Adverse event following Immunization forms (AEFI; <https://vaccine-safety-training.org/classification-of-aefis.html>).

Participants will have the option of donating 12 mL of blood for plasma (serology) and PBMCs for secondary analysis of immune correlates and for future analysis based on covid19-specific IgM and IgG. If they do not donate 12mL of blood, a fingerstick will be required for baseline COVID19 serology.

Dried Blood Spot (DBS): all participants will self-collect DBS samples at week 4, 8, 12, 16, 20 and 24. Envelopes to store the DBS are provided upon enrollment and can be mailed or dropped off at work and picked up by study coordinators.

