COVID specific RNA is found in stool for ~21 days when an individual develops infection (<https://doi.org/10.1038/s41586-020-2196-x>). Participants will have the option of collecting stool swabs monthly if they are asymptomatic or weekly if they develop symptoms. Nucleic acid testing will be performed in retrospect to support secondary objectives.

If participants develop symptoms consistent with COVID19, will be PCR tested for COVID19. They will be given the option of donating 12 mL of blood for plasma and PBMCs 2 weeks after symptoms resolve.

Week 12 (+/- 2 Weeks), participants will be given the option to donate 12 mL of blood for plasma and PBMCs for secondary analysis of immune correlates and for future secondary analysis based on covid-specific IgM and IgG.

Week 24 (+/- 2 Weeks), participants will be given the option to donate 12 mL of blood for plasma and

PBMCs for secondary analysis of immune correlates and for future secondary analysis based on covid-specific IgM and IgG.

Except for the administration of BCG vaccine or placebo and the above mentioned DBS and phlebotomy, participants will undergo no invasive procedures for study purposes.

The following data points will be collected during the follow-up period and at end of study:

Data Variable	
Sore throat (collected at multiple time points)	X*
Fever (collected at multiple time points)	X*
Headache (collected at multiple time points)	X*

Malaise (collected at multiple time points)	X*
Cough (collected at multiple time points)	X*
rt-PCR test for SARS-CoV2 result (as indicated)	X
Serological test for Covid-19 result (every 2 weeks)	X
Number of days ill	X
Daily fever	X
Other Covid-19 symptoms	X
Admitted to hospital	X
Required oxygen	X
Treated in intensive care	X
Required ventilation	X
Death	X
Severe pneumonia	X
Respiratory failure	X
Acute respiratory distress syndrome	X
Sepsis	X
Septic shock	X

**Already being collected as part of routine surveillance of health care workers. Will request access to this information in Informed Consent Form.*

d. Withdrawal of individual subjects/End of Study

Subjects can leave the study at any time for any reason if they wish to do so without any consequences. The investigator can decide to withdraw a subject from the study for urgent medical reasons. Participants who received placebo will be unblinded at the end of the study and pending a recommendation by the DSMB, they will be offered the option of receiving the BCG intervention.

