e. Replacement of individual subjects after withdrawal

A participant will only be replaced in case of withdrawal before the administration of BCG vaccine/placebo.

a. Rationale:

A potential additional benefit of BCG vaccination is the impact of the vaccine on improving cognition and Alzheimer's Disease (AD) outcomes in the presence and absence of COVID19. There are series of published evidence that BCG can improve cognitive outcomes for AD and Parkinson's[16, 17]. Furthermore, there is mounting evidence that COVID-19 can impact the CNS[18-21], as evidenced by the loss of smell and taste reported by many patients as well as the presence of dementia in nearly 40% of patients. Prior pandemics have observed spikes in Parkinson's and other cognitive disorders afterwards[22] and coronaviruses have been associated with Parkinson's[23]. The cognition sub-study would involve cognition baseline and MRI (brain imaging) and follow up at 6 months and 2 years and would include BCG vaccinated, placebo-controlled, COVID-exposed and non-exposed groups. This study design will provide an extremely sensitive and longitudinal measure of cognitive ability that will allow examination of the impacts of COVID-19 and vaccination on the trajectory of mental status.

b. Premature termination of the study

During the study, interim analyses is planned. The safety and futility of the trial will be monitored carefully by the study team and DSMB during these interim analyses. If warranted, the study will be terminated (prematurely). Description of the DSMB and interim analysis is described further below.

8. OPTIONAL COGNITIVE SUB-STUDY (Not available at all sites).

a. Population:

400 subjects enrolled in main BADAS study.

b. Additional Inclusion Criteria:

- Normal or corrected-to-normal vision and hearing (able to see images on computer screen and hear auditory events delivered through the computer speaker).
- >45 years of age.

d. Additional Exclusion Criteria:

- Significant history of mental illness, drug or alcohol abuse; severe trauma preventing normal use of dominant hand (needed to move the mouse cursor); clinical depression (unless medically controlled); other neurologic conditions (i.e. stroke), or learning disability; ophthalmologic/visual problems that prevent viewing a computer screen at a normal distance (such as legal blindness, detached retinas, occlusive cataracts).

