- Having pacemakers, aneurysm clips, cochlear implants, pulse oximeters, EKG leads, or other metal/foreign objects in body or face, making them unable to receive **MRI**.
- <45 years of age.

e. Study Endpoints (Additional to Main Study):

Primary endpoint: incidence of [COVID-19](#)-related cognitive impairment.

Secondary endpoint: severity of cognitive impairment following BCG vaccination compared to placebo that is COVID-19-related.

f. Additional Risks Beyond Main Study:

Minimal risk, MRI and clinical cognitive tests are minimal risk and only involve a small amount of additional time at each visit, expected to be about 2 h in duration, including MRI, with three visits total.

g. Clinical Cognitive Assessment (CCA):

A rapid and sensitive assessment of cognitive status will be accomplished using a cognitive battery with multiple forms designed to identify subtle changes in high functioning medical staff. We have chosen assessments that reduce human cost and produce low variability in data, minimizing potential error. A computer-based process will be used to accomplish high sensitivity and low variability in our cognitive assessments. We will use the NIH Toolbox Cognition Batteries that have strong psychometric assessment capabilities, appropriate procedural considerations, the ability to integrate with REDCap and utilize tablet computer for the process. This system will minimize human factor and related costs with unlimited administrations and scoring capability. We will utilize the ability of NIH Toolbox to assess integrated higher level aspects of cognition where cognitive changes are most impactful, including: attention, working memory, executive functioning and processing speed measures. This strategy will allow us to identify subtle changes in cognitive function due to COVID-19 and the ability of BCG vaccination to mitigate them.

Details for NIH Toolbox Cognition Batteries are available online:

<http://www.healthmeasures.net/explore-measurement-systems/nih-toolbox/intro-to-nih-toolbox/cognition>

h. Magnetic Resonance Imaging (MRI):

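### The cognitive sub-study needs COVID-19 status at its 2-year visit, but scheduled infection detection ends at about day 168 and nothing updates it

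*Combined protocol and SAP*

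**What the plan says.** **The sub-study.** The rationale for the cognitive sub-study is printed at the end of section 7. It sets a baseline assessment and then "follow up at 6 months and 2 years and would include BCG vaccinated, placebo-controlled, COVID-exposed and non-exposed groups". Section 8.e makes the incidence of COVID-19-related cognitive impairment the primary endpoint. The secondary endpoint is "severity of cognitive impairment following BCG vaccination compared to placebo that is COVID-19-related". Section 8 enrols 400 main-study participants and describes three visits, with the NIH Toolbox battery (8.g) and MRI (8.h). It lists no serology, PCR or infection history of its own.

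**Infection detection.** Section 3.a gives main-study follow-up "with a maximum of 168 days" and schedules dried blood spots (DBS) for "serology testing at baseline, weeks 4, 8, 12, 16, 20 and 24". Section 7.c places the weekly symptom survey and the symptom-triggered swab in the same follow-up period. It then states: "If a participant completes the follow-up period and does not test positive for disease, their study participation is complete". For someone who does test positive, "their disease status will be ascertained for up to two months or until an outcome is available". The latest scheduled sample that could inform infection status is an optional one: "Week 24 (+/- 2 Weeks), participants will be given the option to donate 12 mL of blood".

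**What is not stated.** The documents do not define exposed or non-exposed, do not say when exposure is fixed, and give no rule for calling an impairment COVID-19-related.

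**The concern.** Infection status is part of the sub-study outcome. It defines two of the comparison groups and decides which impairments count towards the endpoints. Up to week 24 the main study supplies it. After that nothing does, although cognition and MRI are measured again about 18 months later.

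Two errors follow at the 2-year visit if the plan is carried out as written. A person first infected after main-study follow-up stays in the non-exposed group, which pulls the exposed v non-exposed difference towards zero. Any impairment that follows such an infection cannot be recognised as COVID-19-related, so the primary endpoint is undercounted. The stored data would not show how large either error is.

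The completion rule in section 7.c adds a plain inconsistency. Read literally, it ends participation at 24 weeks for the very people who must return at 2 years as the non-exposed group.

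**Working it through.** The plan offers no figure to reproduce here: the 400 has no stated derivation, and no misclassification rate is given. The check therefore sizes the gap.

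**Inputs from the documents**
- Main-study follow-up: at most 168 days (section 3.a).
- Sub-study size: 400; last visit at 2 years, taken as day 730 (end of section 7; section 8.a).
- Infection by day 168: 5% (section 10.a). This is symptomatic disease, used as a proxy for all infection.

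**Assumption.** The documents give no rate after day 168. Let the later hazard be m times the in-trial hazard, and vary m.

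**Length of the gap**
- 730 − 168 = 562 days; 562/730 = 77%.
- Counting the optional draw to week 26 (day 182): 730 − 182 = 548 days; 548/730 = 75%.

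**Infections inside and outside the window**
- Recorded by day 168: 400 × 0.05 = 20, leaving 380 classed as non-exposed.
- In-trial hazard: h = −ln(0.95)/168 per day.
- Unrecorded by day 730: 380 × (1 − exp(−m × h × 562)) = 380 × (1 − 0.95^(3.345m)), where 562/168 = 3.345.
- Share of infections missed = unrecorded / (20 + unrecorded).
- Share of the non-exposed group misclassified = unrecorded / 380.

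| m (later v in-trial hazard) | Unrecorded | All by day 730 | Share missed | Non-exposed misclassified |
|---|---|---|---|---|
| 0.1 | 6.5 | 26.5 | 24% | 2% |
| 0.25 | 16.0 | 36.0 | 44% | 4% |
| 0.5 | 31.2 | 51.2 | 61% | 8% |
| 1 | 59.9 | 79.9 | 75% | 16% |
| 2 | 110.4 | 130.4 | 85% | 29% |

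**Break-even.** Half of all infections are missed when the unrecorded number also equals 20, a later risk of 20/380 = 5.3% over 562 days. Solving 1 − 0.95^(3.345m) = 0.0526 gives m of about 0.32.

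**Other starting rates.** With 5% v 2% by arm (200 each) and each arm's hazard unchanged, 14 infections are recorded and about 43 are not: 43/57 = 75% missed, and 43/386 = 11% of the non-exposed misclassified. With one common rate and m = 1, 2% by day 168 gives 25.6/392 = 6.5% misclassified, and 10% gives 106.9/360 = 30%. Changing the starting rate at constant hazard barely moves the share missed (73% to 76%). The later hazard is what matters.

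**Effect on the estimates.** Let D be the true difference in impairment between infected and uninfected people, and q the misclassified share. If unrecorded infections carry the same risk as recorded ones, the observed contrast is D × (1 − q), a loss of about 2%, 4% or 16% at m = 0.1, 0.25 or 1. The count of COVID-19-related impairment behaves differently. On the same assumption its shortfall follows the share of infections missed: 24%, 44% or 75%.

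**The case against.** The best counter-argument is that the plan never says exposure must be re-established at 2 years. Section 8.e ties neither endpoint to that visit. One could fix exposure from main-study data, follow both groups for 2 years and treat later infections as contamination. That is a coherent design, but the documents do not state it, and it would still leave later infections in the comparison group and outside the endpoint.

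It can also be said that some information arrives after day 168. The optional week-24 draw may run to day 182. Section 9.b captures serious adverse events, including hospital admissions, until 30 days after the last data collection timepoint, which might extend to the 2-year visit. Routine surveillance of health workers exists outside the study. These narrow the gap, but no section uses any of them to classify exposure, and adverse event reports would miss mild infections. Likewise, an explicit 2-year visit implies that sub-study participants continue despite the completion rule. That is a sensible reading, but it needs to be written down.

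Three stronger readings are tempting and are not supported:
- That most infections will fall in the non-exposed group. This requires a rate after day 168 that the documents do not give, and it fails if the later hazard is below about 0.32 of the in-trial hazard.
- That most of the non-exposed group will have been infected. Even at an unchanged hazard the figure is about 16%.
- That the 2-year results are uninterpretable. Dilution of 2% to 16% in the group contrast is a bias, not a loss of all meaning.

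**Conclusion.** The concern holds in limited form. As written, the sub-study needs COVID-19 status at 2 years and has no scheduled means of obtaining it for about 77% of the interval. This part rests on the text alone.

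The size depends on an assumed later hazard. From one-tenth of the in-trial hazard to no change, 24% to 75% of infections would be missed and 2% to 16% of the non-exposed group misclassified. These figures use symptomatic disease as a proxy for infection, assume no loss to follow-up, and take 5% as the risk across both arms.

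The damage is confined to the 2-year exposed v non-exposed contrast and the 2-year count and severity of COVID-19-related impairment. The 6-month visit is supported by week-24 serology. A randomised BCG v placebo comparison of all cognitive or MRI change does not need infection status, so this gap does not touch it; the possible later offer of BCG to placebo recipients is a separate matter. The main trial is unaffected. For an optional sub-study the point merits a short amendment.

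**What to change.** Define exposed, non-exposed and COVID-19-related impairment in section 8, then choose one of two routes:

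1. **Update exposure at 2 years.** At the visit already planned, collect a dated history of positive COVID-19 tests, hospital care and COVID-19 vaccination, with one DBS card if feasible. Classify exposure from this together with the main-study data. Vaccination history belongs there because section 10.f anticipates a specific vaccine, which could complicate the reading of a late antibody result.
2. **Fix exposure at week 24.** State that exposure is set by main-study data to week 24, and restrict the COVID-19-related endpoints to the 6-month visit.

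Under either route, state that the completion rule in section 7.c does not end participation for those in the sub-study.

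The first route costs a few questions and possibly one fingerstick, of a kind already used, for 400 people. It would still miss some late infections through poor recall or faded antibodies. The second adds no data collection but gives up the 2-year COVID-19-related endpoints. Both need a sub-study amendment.

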10. SAMPLE SIZE AND STATISTICAL ANALYSIS

Data will be reported quantitatively. All analyses will be performed from the intention-to-treat principle. Missing data will be dealt with by multiple imputation using the mice package in R.

a. Sample size calculation

The study in the United States will include at least three sites: Houston (BCM and MD Anderson Cancer Center considered as 'one site' due to proximity), Texas A&M University (TAMU), and Cedars Sinai Medical Center (CSMC). TAMU will enroll 1400 individuals. The proposed enrollment sample size is designed to provide 80% power to detect a 60% vaccine efficacy (a relative risk of 0.4 among the vaccinated). This is based on the observed three-fold decline in respiratory infections in the South Africa adolescent cohort with 80% power and 0.05 type 1 error in a two-tailed test. We expect 5% of study participants to develop symptomatic COVID19 during follow-up, therefore a sample size of 1400, with 700 receiving intervention and 700 receiving placebo. We do not expect significant loss to follow up among HCWs (there has been zero LTF after the first 500 participants). We will plot Kaplan-Meier curves comparing COVID19 disease between the BCG and placebo groups and report hazard ratios and p-values using Cox proportional hazard models. DBS samples will be collected at baseline and weeks 4, 8, 12, 16, 20 and 24 post intervention. PBMCs and plasma donations are optional at baseline, 12 and 24 weeks. If interim analysis identifies a large proportion of participants to be seropositive before intervention, power analysis will be evaluated and an amendment will be submitted if additional participants need to be recruited.

b. Interim analysis

One month after the first 100 participants are enrolled, an interim analysis will be held by the independent statistician of the trial. Data will be exported independently from all sites and then data collated and merged for the interim analysis). The above described statistical analysis will be evaluated as well as safety profile. Enrollment is expected to occur within the first two months of launch. Interim analysis will occur based on study enrollment and three to six interim analysis will occur based on temporal dynamics of enrollment as requested by the DSMB. We will stop the clinical trial early if the p-value of any interim analysis is smaller than the pre-specified type-1 error cutoff. Each interim analyses will be reported to the DSMB.

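### The cognitive sub-study's 2-year BCG v placebo comparison comes after allocation is released, and the plan neither records nor handles any BCG taken later by placebo recipients

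*Combined protocol and SAP*

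**What the plan says.** The sub-study rationale (placed at the end of section 7) sets a baseline assessment and "follow up at 6 months and 2 years". Section 8.f confirms the count, "with three visits total". The rationale says the sub-study "would include BCG vaccinated, placebo-controlled, COVID-exposed and non-exposed groups". Section 8.a gives its size as "400 subjects enrolled in main BADAS study". Section 8.e lists as the secondary endpoint "severity of cognitive impairment following BCG vaccination compared to placebo that is COVID-19-related", without naming a visit.

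The main study is much shorter. Section 3.a limits each participant's follow-up, "with a maximum of 168 days". Section 7.c adds up to two months of outcome tracking for anyone who tests positive.

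Two places govern unblinding. Section 7.a releases allocation to all participants at the end of the study, once the analysis is complete. Section 7.d unblinds placebo recipients at the end of the study and says that, subject to a DSMB recommendation, "they will be offered the option of receiving the BCG intervention".

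End of study is defined in section 3.a, in section 7.a and in section 12 (Temporary halt and end of study report). Each time it is the last participant's final entry in the app or data capture system. None of the three mentions the sub-study.

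**The concern.** The 2-year visit is one of only two assessments after baseline, so it carries much of what the sub-study says about the course of cognition over time. If allocation is known by then, two things follow. Knowledge of allocation can affect who returns and how they perform on tests that depend on effort. It can also affect MRI reading, because section 8.h includes visual rating scales. In addition, if placebo recipients take BCG, the 2-year placebo group becomes a mixture of people who never had BCG and people who had it late.

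The plan gives no analysis for the sub-study, does not assign the BCG v placebo endpoint to a visit, has no field for BCG received after the main study, and does not say how crossover would be handled. Followed as written, it yields a 2-year comparison whose departure from the randomised, blinded design could not be described afterwards.

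**Working it through.** The question is whether release of allocation comes before the 2-year visits. Time is in months from launch, with 30.44 days per month.

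**Inputs**
- Enrolment, section 10.b: "Enrollment is expected to occur within the first two months of launch", so 2 months.
- Main follow-up, section 3.a: 168 days. This agrees with the last dried blood spot at week 24: 24 × 7 = 168. In months, 168 / 30.44 = 5.5.
- Tracking of positive cases, section 7.c: up to 2 months.
- Final DSMB review, section 9.c: two to four months after study completion.
- Final study report, section 12: within 12 months of the end of study. I take this as the latest date by which the analysis is complete (assumption).

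**When allocation could be released**
- End of study: 2 + 5.5 = 7.5, or 7.5 + 2 = 9.5 with positive cases tracked to the limit.
- Latest final DSMB review: 9.5 + 4 = 13.5.
- Latest final report: 9.5 + 12 = 21.5.

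**When the 2-year visits fall**
- First participant: 0 + 24 = 24.
- Last participant: 2 + 24 = 26.

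**Interval from release to the earliest 2-year visit**
- From end of study: 24 − 9.5 = 14.5 months.
- From the latest DSMB review: 24 − 13.5 = 10.5 months.
- From the latest final report: 24 − 21.5 = 2.5 months.

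Release precedes every 2-year visit on each of these readings.

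**Sensitivity to slower enrolment.** For the first participant's 2-year visit to precede the latest report date, enrolment would have to exceed 24 − 5.5 − 2 − 12 = 4.5 months. For the last participant enrolment time cancels, so that participant's 2-year visit follows the latest report date by the same 4.5 months whatever the pace.

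**The 6-month visit.** Six months is 6 × 30.44 = about 183 days, roughly two weeks beyond the 168-day limit. The first participant reaches it at month 6, before end of study at 7.5. The last reaches it at 2 + 6 = 8, slightly after 7.5 if no positive case extends the study. It is therefore largely protected but not guaranteed, and early stopping could bring release forward.

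**The case against.** The strongest reply is that end of study means the last entry in the data capture system. Section 8.g says the cognitive battery can integrate with REDCap, so the 2-year entries might themselves postpone end of study and with it unblinding. The 168-day limit does not settle this, because it is tied to the main primary endpoint and a 2-year visit exceeds it on any reading. The reply stands as an ambiguity. But the plan never says it. It also sits poorly with section 7.c, under which participants who stay negative finish the study when follow-up ends, and with section 10.k, which hopes to extend a positive result to placebo participants quickly.

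A reader might go further and infer that the 2-year comparison is certain to be contaminated by crossover. The documents do not support that. The offer depends on the DSMB and acceptance is optional, so after a null or unfavourable result there may be no crossover.

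A reader might also infer that unblinding comes more than a year before the 2-year visit. That holds only if it happens at end of study itself. Section 7.a waits for the completed analysis, and the interval can then be as short as 2.5 months.

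Loss of blinding may also matter less than it seems. Testing is computer-based and MRI reading is partly automated. Section 9.b says nearly all BCG recipients develop redness and a small pustule, so many may guess their allocation within weeks, and the 6-month visit is exposed to this too. These points reduce the added harm of formal unblinding but do not remove it. They do not touch the missing record of later BCG.

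**Conclusion.** The concern holds in a limited form. On the plan's own timings the 2-year BCG v placebo comparison will be unblinded. This rests on two-month enrolment, an analysis completed no later than the final report, and an end of study that does not include the 2-year visits. Dilution by crossover is possible but conditional.

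Its size cannot be derived from the documents. One could be tempted to shrink a standardised difference by the share of placebo recipients who take BCG, with about 200 per arm. That would assume a continuous outcome in all 400 participants and a late dose that reproduces the full effect of an early one. The sub-study endpoints concern only COVID-19-related impairment, and at the 5% symptomatic rate in section 10.a about 400 × 0.05 = 20 participants would be symptomatic cases during main follow-up. A late dose cannot prevent infections that have already happened. No such figure is offered here.

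Nor does the lack of a named visit show that the two time points were meant to carry equal weight; the plan is silent. The main trial's conclusions are unaffected. For an optional sub-study this is worth correcting, because as written the 2-year result could not be interpreted properly after the event.

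**What to change.** 1. Reconcile the end-of-study definition with the 2-year sub-study visit, and state when sub-study participants learn their allocation relative to that visit.
2. Record whether and when each sub-study participant receives BCG after the main study.
3. Name the 6-month assessment, completed before that participant's allocation is released, as the blinded randomised BCG v placebo comparison.
4. Report the 2-year comparison by randomised group, in line with the intention-to-treat statement in section 10, and give the loss of blinding and the proportion of placebo recipients who took BCG alongside it.

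The cost is some sub-study wording and one extra data field; no visit is added. The downside is that the 2-year BCG v placebo result becomes supportive, which gives up some of the sub-study's emphasis on long-term course.
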